4.2 Concomitant Medications/Treatments

Concomitant medications allowable as deemed appropriate by treating physicians.

4.3 Duration of Therapy

End of protocol therapy will be the last day of radiation. Other exceptions may apply:

- Disease progression
- Inter-current illness that prevents further administration of treatment
- Unacceptable adverse event(s)
- Subject decides to withdraw from the study, **OR**
- General or specific changes in the patient's condition render the subject unacceptable for further treatment in the judgment of the investigator".

4.4 Duration of Follow Up

No follow-up required for this study after radiation completed.

4.5 Removal of Subjects from Protocol Therapy

Subjects will be removed from therapy when any of the criteria listed in Section 5.5 apply. Notify the Principal Investigators, and document the reason for study removal and the date the subject was removed in the Case Report Form. The subject should be followed-up per protocol.

4.6 Subject Replacement

If a subject is withdrawn from the study prior to completing radiation therapy due to standard concerns for treatment side effects, an additional subject may be added. Notify the Principal Investigators, and document the reason for study replacement and the date the subject was removed in the Case Report Form.

5.0 STUDY PROCEDURES**5.1 Screening/Baseline Procedures**

Assessments performed exclusively to determine eligibility for this study will be done only after obtaining informed consent. Assessments performed for clinical indications (not exclusively to determine study eligibility) may be used for baseline values even if the studies were done before informed consent was obtained.

All screening procedures must be performed within 60 days prior to registration unless otherwise stated. The screening procedures include:

5.1.1 *Informed Consent***5.1.2 *Medical Diagnosis*****5.1.3 *Demographics***

Age

5.1.4 *Review subject eligibility criteria***5.1.5 *Physical exam including vital signs, height and weight***

Vital signs (temperature, pulse, respirations, blood pressure) for each protocol related visit.

5.1.6 *Adverse event assessment*

None

5.1.7 *Pregnancy test (for females of child bearing potential)*

See section 3.1.3 for definition. This is done prior to enrollment. Patients may refuse testing if they attest they are not pregnant.

5.1.8 *Breathing evaluation*

Treatment target motion, surface motion and breathing duration will be evaluated before SBRT (does not have to be done prior to registration). The following screening procedures will be pursued sequentially:

1. Free-breathing tumor motion evaluation: imaging will be acquired and physician will determine whether tumor motion > 5 mm.
2. For those patients with tumor motion > 5 mm, breath-holding duration will be evaluated. At this stage, patient will be positioned supine in a stable position. Patient will be asked to breathe oxygen-enhanced air and then take deep inspiration breath hold. Ask patient to repeat breath-holding 3 times and record breath-holding time. If patients can hold breath ≥ 30 seconds in all three times, patients will be eligible for the study.
3. Patient will be monitored by optical cameras to assess surface motion. Air tube will be setup to assist oxygen-enhanced air breathing. ***Care must be taken to ensure tubing is not over patient chest, as optical cameras will acquire surface images for motion evaluation.*** Patient will be instructed to conduct DIBH and optical cameras will monitor patient surface during breath hold. If surface motion > 5 mm during the breath hold, patient will not be qualified for this trial. Another test is that we will instruct patient to repeat breath hold three times. If patient is able to repeat breath hold to the level of the first setting within 5 mm tolerance, patient will move on for the further study step.
4. DIBH tumor motion evaluation: after surface motion evaluation, DIBH tumor motion evaluation will be conducted under imaging one more time. Imaging will be acquired and physician will determine whether tumor motion ≤ 5 mm in one direction.

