DIBH qualified patient will experience one high-resolution CT scan as SOC and additional lower dose CT scans to further investigate inter-DIBH patient surface and tumor position stability and repeatability.

1. Spirometer will be used to select DIBH level and monitor DIBH status during CT simulation. One SOC high-resolution CT will be acquired in single DIBH duration. Within 10 minute, a low-resolution/low-dose CT image in single DIBH duration will be acquired. This study is to quantify inter-DIBH tumor position and patient surface repeatability.
2. Patient will then be scanned using a lower dose CT protocol with DIBH level set at $\pm 10\%$ deviated from the selected DIBH level. This study is to find the correlation between DIBH level and tumor position /chest-abdomen surface level.

The SOC DIBH CT scan will be transferred to Eclipse treatment planning system for treatment planning. Tidal volume measured by spirometer and DIBH surface from CT image will be used as a reference surface for patient treatment initial setup. CBCT will be acquired before each fractional treatment for the patient alignment before beam delivery.

During the treatment delivery, patient will perform DIBH while AlignRT system monitors patient surface. As a pilot study, we will also use spirometer to monitor patient breath-hold tidal volume, and imaging acquired in any two DIBH periods to quantify inter- and intra- DIBH tumor position variation. Following our SBRT treatment protocol, patient will get CBCT scan before the last beam delivery. We will follow the same protocol to acquire CBCT images. These CBCT images will be used to evaluate treatment dose variation to quantify treatment delivery accuracy.

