5.2 Procedures during Treatment

5.2.1 CT simulation

- CT Simulation scans at DIBH will be assisted by spirometer ---must ensure tubing from spirometer not over chest wall so skin rendering is able to be reproduced.
- CT simulation scan (full-length) will be acquired with at a single DIBH duration, starting at least 10 cm above the superior extent of tumor and continuing on every CT slice to at least 10 cm below the inferior extent of the tumor. DIBH signal will be monitored by spirometer. If there is no contraindication to contrast administration, patient will receive DIBH CT scans with contrast administration.
- CT acquisition should be done with gantry 0 degree with spacing ≤ 2 mm.
- Additional DIBH CT scans will be conducted using lower dose CT scan protocol. One at the same DIBH level and the other two will be $\pm 10\%$ deviated from DIBH breath level

- All images will be transferred to the treatment planning computers for tumor motion evaluation and planning.

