5.2.2 Tumor motion evaluation and target volume delineation

On the acquired four different DIBH CTs, gross tumor volume (GTV) will be contoured by an appropriately trained physician. Tumor center point (center of mass) will be the identified and used for motion evaluation. Both inter- and intra- motion amplitude will be analyzed and margins will be estimated. The acquired high-resolution DIBH CT will be used as a primary image for planning. Physician will expand the GTV to PTV by adding proper size margins.

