5.4 Time and Events Table

	Pre-study	Treatment
Assessment		
Informed Consent	X	
History and PE ^A	X	X ^C
Pregnancy Test ^B	X	
CBCT scans		X

^A include vital signs

^B Recommended but patient may refuse if they attest they are not pregnant

^C Only vital signs, once per week

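### Minor: the pregnancy check can be 60 days old or older when the study-added CTs begin, and no repeat is scheduled; tie it to imaging instead of registration

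*Combined protocol and SAP*

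**What the plan says.** All references are to the combined protocol and SAP.

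- **Window.** Section 5.1: "All screening procedures must be performed within 60 days prior to registration unless otherwise stated". Section 5.1.7 places the pregnancy test before enrollment and gives no shorter limit.
- **Refusal.** Section 5.1.7: "Patients may refuse testing if they attest they are not pregnant". Footnote B of the table in 5.4 agrees: "Recommended but patient may refuse if they attest they are not pregnant". Neither dates the attestation. The table marks the test under Pre-study only.
- **Imaging after registration.** The breathing and motion evaluation in 5.1.8 "does not have to be done prior to registration"; its only time limit is that it precedes SBRT. Step 4 adds that "DIBH tumor motion evaluation will be conducted under imaging one more time". No modality is named.
- **Study-added CTs.** Section 4.1: "DIBH qualified patient will experience one high-resolution CT scan as SOC and additional lower dose CT scans". Section 5.2.1: "Additional DIBH CT scans will be conducted using lower dose CT scan protocol", one at the same breath-hold level and two at 10% above and below it. Section 5.2.2 confirms the total: "On the acquired four different DIBH CTs".
- **Safeguards.** Pregnancy is an exclusion (3.2.1). All criteria must be met for registration (3.0) and confirmed beforehand (8.3). Section 3.1.3 requires agreement to contraception from before study entry to the end of study imaging, and immediate notice of a suspected pregnancy. Section 5.5.7 lists pregnancy as a reason for removal.
- **Definition.** The sub-item under 3.1.3 (numbered 3.1.6.1) defines child-bearing potential by two negative bullets, no relevant surgery and no natural menopause of at least 12 months, joined by 'or'.

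**The concern.** The pregnancy test is the only objective check the protocol names behind exclusion 3.2.1, which exists because of fetal risk. Its date is tied to registration, but the exposure the study adds comes later, at an unspecified distance. SBRT and one simulation CT are standard of care; the three lower-dose CTs are there because of the study. For those the study should supply a current check, and as written it need not be current. At stake is fetal exposure in a woman whose pregnancy nobody has recognised. The analysis is not affected.

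The definition raises a smaller question. With 'or' between two negative conditions, a woman needs to satisfy only one of them to count, so women who cannot conceive are swept into the contraception and testing rules.

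**Working it through.** The plan states no figure to reproduce here. The check is date arithmetic, a count of scans and a truth table.

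**1. Age of the test.** Inputs: window of 60 days before registration (5.1); g = days from registration to the imaging in question, with no cap in 5.1.8 or 5.2.1. Maximum permitted age = 60 + g. The values of g are assumptions.

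| g (days) | 0 | 7 | 14 | 28 |
|---|---|---|---|---|
| Maximum age (days) | 60 | 67 | 74 | 88 |

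Sixty days is 60 / 30.4375 = 1.97 months. If the before-enrollment phrase in 5.1.7 is read as an exception to the general window, even the 60-day bound goes. If motion imaging is done before registration, the test may be younger at that imaging.

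**2. Study-added CTs.** 4 breath-hold CTs (5.2.2) − 1 standard-of-care CT (4.1) = 3.

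**3. Part of that age outside the contraception rule.** The g days after registration are covered by 3.1.3. The days before it depend on what 'study entry' means, which the protocol does not define.

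- If it means registration, the uncovered part is at most 60 days, whatever g is.
- If it means consent, and the test is done only for eligibility, the test must follow consent (5.1), so the uncovered part is near zero. A clinically indicated test may precede consent (5.1) and would not benefit from this.

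**4. Effect of a limit of w days before imaging.** The age at imaging is then at most w. On the registration reading, the uncovered part is max(0, w − g):

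| g (days) | 0 | 7 | 14 | 28 |
|---|---|---|---|---|
| Current rule | 60 | 60 | 60 | 60 |
| w = 14 (assumed) | 14 | 7 | 0 | 0 |
| w = 7 (assumed) | 7 | 0 | 0 | 0 |

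The reduction is 60 − 14 = 46 to 60 − 0 = 60 days of permitted time. It applies only on the registration reading; on the consent reading there is little to reduce.

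**5. Refusal.** If a share r of these women decline the test, a date rule gives a recent test in 1 − r of them. Assumed r = 0, 25 or 50% gives 100, 75 or 50%.

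**6. Definition, main clauses only.**

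| Surgery | Naturally postmenopausal ≥ 12 months | With 'or' | With 'and' |
|---|---|---|---|
| No | No | counts | counts |
| No | Yes | counts | does not |
| Yes | No | counts | does not |
| Yes | Yes | does not | does not |

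As written, 3 of 4 combinations count as child-bearing; with 'and', 1 of 4. The two extra rows are naturally postmenopausal women without surgery, and women after surgery who are not naturally postmenopausal.

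**The case against.** The strongest reply is that nothing here contradicts anything else. The protocol sets no shorter standard that the 60-day window breaches, and it has other protections. A woman known to be pregnant cannot be registered however old her test is (3.2.1, 3.0, 8.3), and contraception, self-report and removal follow. The test can be declined, so a date rule tightens an optional check. The trial has 10 patients, and the documents do not say how many are women who could conceive. Section 5.1.8 does not say whether the motion imaging is study-added or standard of care, or whether it uses ionising radiation.

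Much of this stands. It confines the gap to unrecognised pregnancy and makes the three lower-dose CTs the only exposure the documents clearly attribute to the study. It does not remove the gap: none of the safeguards is a test, self-report and removal act only once pregnancy is suspected or known, and no contraception start date is tied to the test. Refusal limits the benefit, but a fresh dated attestation is still better than an undated one.

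A reader might infer that the plan lets pregnant women enter the trial. It does not; pregnancy is a stand-alone exclusion to be confirmed before registration. A reader might also take the 46 to 60 days as a reduction in risk. It is permitted calendar time, under one reading of an undefined term and with assumed values of g and w.

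**Conclusion.** The timing point holds as a minor patient-safety improvement. The protocol permits a test 60 + g days old, with g uncapped, when the three study-added CTs begin, and an attestation with no date. This is a permitted worst case, not a prediction of practice: routine checks before simulation may exist, but the protocol mentions none. The uncovered time before registration ranges from near zero to at most 60 days, depending on the meaning of 'study entry' and on whether the test was done only for eligibility. The number of women affected cannot be worked out from the documents.

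The definition point is a genuine logical slip without a safety cost. A reader might infer that it lets fertile women escape testing; the truth table shows the opposite, since 'or' only over-includes. The burden is small because abstinence counts as contraception and the test can be declined. Neither point touches the feasibility endpoint or the analysis.

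**What to change.** **Timing.** In 5.1.7, take the pregnancy test out of the 60-day window. Require it, or a fresh dated attestation if it is refused, within a short interval set by the investigators (for example 7 to 14 days, an assumption) before the first protocol imaging that uses ionising radiation, and in any case before the study-added CTs. Keep the check before enrollment, repeat it if imaging slips past the interval, and mark this in the 5.4 table. Wording the trigger this way means it works whatever modality 5.1.8 turns out to use.

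**Definition.** Under 3.1.3, change 'or' to 'and' between the bullets, and qualify the bracketed remark about menses so that natural menopause governs. The second edit is needed: with 'and' alone, that remark could drop a fertile woman whose menses stopped for another reason, such as the hormonal contraception that 3.1.3 allows.

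**Cost.** One amendment with five edits (interval, repeat rule, attestation date, 5.4 table, definition). It needs IRB approval before use (8.6), so it is best joined to the next amendment. The practical downside is an occasional repeat test when imaging is delayed. The definition edit takes both over-included groups out of the child-bearing category and so out of its testing and contraception rules.

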5.2 Procedures during Treatment

5.2.1 CT simulation

- CT Simulation scans at DIBH will be assisted by spirometer ---must ensure tubing from spirometer not over chest wall so skin rendering is able to be reproduced.
- CT simulation scan (full-length) will be acquired with at a single DIBH duration, starting at least 10 cm above the superior extent of tumor and continuing on every CT slice to at least 10 cm below the inferior extent of the tumor. DIBH signal will be monitored by spirometer. If there is no contraindication to contrast administration, patient will receive DIBH CT scans with contrast administration.
- CT acquisition should be done with gantry 0 degree with spacing ≤ 2 mm.
- Additional DIBH CT scans will be conducted using lower dose CT scan protocol. One at the same DIBH level and the other two will be $\pm 10\%$ deviated from DIBH breath level

- All images will be transferred to the treatment planning computers for tumor motion evaluation and planning.

5.2.2 Tumor motion evaluation and target volume delineation

On the acquired four different DIBH CTs, gross tumor volume (GTV) will be contoured by an appropriately trained physician. Tumor center point (center of mass) will be the identified and used for motion evaluation. Both inter- and intra- motion amplitude will be analyzed and margins will be estimated. The acquired high-resolution DIBH CT will be used as a primary image for planning. Physician will expand the GTV to PTV by adding proper size margins.

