2.0 STUDY OBJECTIVES

2.1 Primary Objectives

2.1.1 To investigate the feasibility of applying VRT-DIBH to lung/liver cancer SBRT

2.2 Secondary Objectives

2.2.1 To determine planning target volume margin by investigating tumor residual motion in VRT-DIBH

2.2.2 To determine VRT surface monitoring threshold by investigating inter/intra VRT-DIBH patient surface stability/reproducibility/sensitivity

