5.2.8 Post-Radiation analysis

- Analyze recorded daily AlignRT treatment setup delta values
- Analyze recorded daily position shift using CBCT alignment
- Analyze recorded daily AlignRT treatment delta values, investigate surface stability and reproducibility
- Delineate tumor on recorded CBCT images and investigate the position error
- Project treatment beams on CBCT images and recalculate dose with CBCT images. Evaluate dose difference between the planned and the delivered.
- Treatment time analysis

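### The PTV margin analysis in section 5.2.2 names only center-of-mass displacement, so rotation and symmetric shape change of the tumor between breath-holds are not measured and the margin may be understated for elongated or deforming tumors

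*Combined protocol and SAP*

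**What the plan says.** Section 2.2.1 sets the secondary objective: "To determine planning target volume margin by investigating tumor residual motion in VRT-DIBH". Section 2.4.2 lists the target margin as an endpoint.

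Section 5.2.2 gives the method. The full tumor is outlined on every simulation scan: "On the acquired four different DIBH CTs, gross tumor volume (GTV) will be contoured by an appropriately trained physician". One point is then taken from each outline: "Tumor center point (center of mass) will be the identified and used for motion evaluation". The margin follows from that: "Both inter- and intra- motion amplitude will be analyzed and margins will be estimated". The expansion used for planning is described separately: "Physician will expand the GTV to PTV by adding proper size margins". No size is given for it, and nothing ties it to the center-of-mass result.

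Under section 5.2.1 the four scans are the planning CT, one low-dose repeat at the same breath level, and two low-dose scans set deliberately 10% above and below that level.

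Section 5.2.8 adds treatment-time data: "Delineate tumor on recorded CBCT images and investigate the position error" and "Project treatment beams on CBCT images and recalculate dose with CBCT images". Section 6.3, the data analysis plan, speaks of tumor position accuracy and dosimetric accuracy. Neither section defines a tumor rotation, overlap or surface-distance measure, and no section gives a margin formula.

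**The concern.** A margin is a statement about edges: the expanded planning GTV has to contain the tumor as it lies in a later breath-hold. The center of mass is one point. If the tumor turns about that point, or lengthens along one axis while narrowing along another, the point stays put and the edge moves outside the planned outline. A margin built only from center-of-mass displacement has no term for this.

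The protocol itself gives a reason to look. Section 1.2 cites a report that, at the same vital capacity, abdominal and thoracic breathing differed by 1.9 cm on average in chest wall expansion. Equal spirometer readings therefore need not mean equal anatomy. That report, as cited, concerns the chest wall and does not show that tumors rotate or deform.

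At stake is the usefulness of the margin endpoint. If the estimate is carried into a later trial, a missing component would make it too small for the tumors in which that component is largest.

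**Working it through.** The plan states no margin value or formula, so there is no figure to reproduce. The check is geometric: how far can the edge move while the center of mass moves 0 mm?

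**Inputs**
- From the documents: center of mass as the only motion measure named for the simulation CTs (5.2.2); a 5 mm limit on tumor position variation within and between breath-holds (4.1), used only for scale.
- Assumed, because the documents give none: an elliptical tumor section with long semi-axis *a* = 15 to 25 mm and short semi-axis *b* = 10 mm; rotation θ = 3 to 10 degrees; a symmetric stretch of 10% along the long axis with matching compression across it.

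**Step 1: rotation about the center.** The uniform expansion of the original ellipse needed to contain the rotated one is (*a* − *b*) × sin θ. A numerical comparison of the two outlines gives the same values.

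| *a* × *b* (mm) | 3° | 5° | 10° |
|---|---|---|---|
| 10 × 10 | 0 | 0 | 0 |
| 15 × 10 | 5 × 0.0523 = 0.26 | 5 × 0.0872 = 0.44 | 5 × 0.1736 = 0.87 |
| 20 × 10 | 10 × 0.0523 = 0.52 | 10 × 0.0872 = 0.87 | 10 × 0.1736 = 1.74 |
| 25 × 10 | 15 × 0.0523 = 0.79 | 15 × 0.0872 = 1.31 | 15 × 0.1736 = 2.60 |

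The center-of-mass shift is 0 mm in every cell. For the elongated shapes the unmeasured part runs from 0.26 to 2.60 mm.

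The simpler formula, *a* × sin θ, should not be used. It gives the travel of the tumor's tip and ignores the tumor's width. For 25 mm and 10 degrees it returns 25 × 0.1736 = 4.34 mm instead of 2.60 mm, and for a round tumor it returns a positive value where the answer is 0.

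**Step 2: symmetric stretch.** The edge on the long axis moves by 0.10 × *a*: 1.0 mm at *a* = 10 mm, 1.5 mm at 15 mm, 2.0 mm at 20 mm and 2.5 mm at 25 mm. The center again moves 0 mm. This applies to round tumors too.

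**Step 3: one-sided change.** Let a tumor of 10 mm radius bulge by 3 mm on one side, modeled as two half-ellipsoids of height 13 and 10 mm. The center of mass moves (3/8) × (13² − 10²) / (13 + 10) = (3/8) × 69 / 23 = 1.1 mm. The measure sees about 1.1 of the 3 mm, so asymmetric change is partly captured.

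**Scale.** The upper values in steps 1 and 2 are about half of the protocol's 5 mm limit (2.6 / 5 = 0.52; 2.5 / 5 = 0.50).

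**The case against.** The strongest reply is that nothing is lost. Full contours exist on all four CTs, the tumor is delineated again on the treatment CBCTs, and recalculating dose on those images could reveal lost coverage. A reader might infer from section 5.2.2 that rotation and deformation cannot be seen in this study. The documents do not support that: the data are collected, and asymmetric change moves the center of mass in part. What remains is that no section names a measure that would extract the information, or feeds the CBCT position error or recalculated dose back into the margin estimate. The dose comparison serves an exploratory objective (2.3.1).

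A second reply is that no bias can be assigned to an unwritten formula. This stands against the stronger inference that the estimated margin *is* too small. The eventual formula could include a separate shape term, and contouring differences or the two scans at shifted breath levels could push the estimate upward. But no such term is written, and an unrelated upward error is not a correction for a missing component.

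Third, a reader might infer that study patients would be underdosed. That does not follow: section 5.2.2 leaves the treatment margin to the physician and does not link it to the center-of-mass result.

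Last, the effect may be small. That also stands: in step 1, tumors of 20 × 10 mm or less, rotated by 5 degrees or less, stay under 1 mm.

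**Conclusion.** The point holds in a limited form. Center of mass is the only tumor-motion measure that section 5.2.2 names for the margin estimate. It does not register rotation about the center or symmetric change of shape, and it registers asymmetric change only in part. The study's margin may therefore be understated for elongated or deforming tumors.

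The unmeasured part is about 0.3 to 2.6 mm for the assumed elongated tumors under rotation, 0 mm for a round tumor under pure rotation, and about 1.0 to 2.5 mm for an assumed 10% stretch. These sizes rest wholly on assumed dimensions, angles and stretch. Whether the final margin would be materially wrong cannot be settled from the documents. This is a worthwhile, cheap improvement to a descriptive secondary endpoint in 10 patients. It is not a safety finding about how those patients are treated.

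**What to change.** In sections 5.2.2 and 5.2.8, for each repeat breath-hold CT and each CBCT at the planned breath level, report two quantities from the contours already planned:

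- (a) the center-of-mass shift in each direction;
- (b) the expansion of the planning GTV in each direction needed to enclose the repeat GTV **after** the two centers of mass are aligned.

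Aligning first keeps the rotation and shape component separate. An enclosing expansion taken without alignment already contains the shift, so combining it with (a) would count the shift twice. Judge enclosure over the whole surface, not from the tumor's extreme extents along the three axes, because a rotated edge moves most in an oblique direction. For the 25 × 10 mm case at 10 degrees, with the long side along an axis, the extent across that axis grows only by √(25² sin² 10° + 10² cos² 10°) − 10 = 10.76 − 10 = 0.76 mm, against the 2.60 mm needed.

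State the margin formula, and present the study's margin estimate with and without (b). Keep the two scans at ±10% breath level out of it, since they were displaced on purpose to study the relation between breath level and position.

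The cost is analysis time; no new scan is needed and no treatment rule changes. The downside is that (b) is a worst-edge measure. It includes contouring differences between the planning CT, low-dose CT and CBCT, so it tends to be an upper estimate and should be labeled so. Each patient has only one repeat CT at the planned level, so most of the information on (b) will come from the CBCTs, and the two sources should be shown separately.

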2.3.2 Treatment time

2.4 Endpoints

2.4.1 VRT-DIBH feasibility

2.4.2 To determine target margin in VRT-DIBH lung/liver SBRT

2.4.3 To determine threshold used for surface monitoring in VRT-DIBH assisted lung/liver SBRT

3.0 PATIENT ELIGIBILITY

Eligibility waivers are not permitted. Subjects must meet all of the inclusion and exclusion criteria to be registered to the study. Study treatment may not begin until a subject is registered.

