4.0 TREATMENT PLAN

4.1 Treatment Dosage and Administration

Patient recruit on this treatment protocol will go through training-screening sessions:

1. Patient will go through a tumor motion evaluation session. Since we would like to test the effectiveness of our proposed motion management strategy, we would like to recruit patient with tumor motion in one direction is larger than 5 mm. Tumor motion in free-breathing mode will be evaluated under imaging study..
2. Patient will go through a pre-oxygenation training-screening session. Research studies^{18, 19} already shown that pre-oxygenation can effectively prolong breath-holds in patients with cancer. In this study we will combine patient training, screening, and pre-oxygenation to prolong patient breath-hold duration in radiotherapy procedure. Patient will be asked to breathing oxygen-enhanced air through a facial mask and take deep inspiration breath hold. We will use spirometer to find the maximum deep inspiration breath level and set a comfortable/optimal breath hold level ~75% of the maximum deep inspiration. Only patient can have single DIBH duration \geq 30 seconds will be eligible for the study.
3. Patient will go through a real-time coaching training session assisted by DIBH technique. After being trained, patient will go through motion assessment section. Patient will be set on treatment couch with chest exposed which allows cameras catch patient body surface information. Spirometer will be used to assist DIBH setup. Optical camera system will be used to acquire patient chest/abdomen surface. During the surface image acquisition, imaging will be used to acquire tumor position or diaphragm position. The surface images and tumor positions acquired in single DIBH durations will be used to quantify intra-DIBH patient surface and tumor position stability. The surface images and tumor positions acquired across several DIBH durations will be used to quantify inter-DIBH patient surface and tumor position repeatability. The intermittent time between DIBH durations can be varied between 1-10 minutes.
4. Only patient with inter/intra-DIBH tumor position variation \leq 5 mm and inter/intra-DIBH surface level variation \leq 5 mm will be move on for this VRT-DIBH protocol study. Otherwise, patients will be off study and treated per standard of care.

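### Does the target-margin endpoint need a written rule for turning breath-hold motion into a margin?

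*Combined protocol and SAP*

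**What the plan says.** Objective 2.2.1 is "To determine planning target volume margin by investigating tumor residual motion in VRT-DIBH", and endpoint 2.4.2 is "To determine target margin in VRT-DIBH lung/liver SBRT". Section 5.2.2 has the GTV contoured on four DIBH CTs, uses its centre of mass as the motion measure, and then states: "Both inter- and intra- motion amplitude will be analyzed and margins will be estimated". The same paragraph leaves the expansion from GTV to PTV in each plan to the physician.

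Section 4.1 gives most of the motion data a purpose:

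- **Screening, within a hold:** "The surface images and tumor positions acquired in single DIBH durations will be used to quantify intra-DIBH patient surface and tumor position stability". Images across several holds serve inter-DIBH repeatability.
- **Repeat CT at the same level:** "This study is to quantify inter-DIBH tumor position and patient surface repeatability".
- **CTs at levels 10% above and below:** "This study is to find the correlation between DIBH level and tumor position /chest-abdomen surface level".
- **Treatment delivery:** "imaging acquired in any two DIBH periods to quantify inter- and intra- DIBH tumor position variation".

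Step 4 of the training and screening sequence sets the limit for continuing: "Only patient with inter/intra-DIBH tumor position variation" of no more than 5 mm, with the same limit for the surface. Section 6.2 plans descriptive statistics for motion, surface and dose. Sections 5.2.8 and 6.3 cover tumour position and recalculated dose on CBCT. Section 6.0 judges feasibility by whether 50% of enrolled patients finish breath-holding SBRT.

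**The concern.** A margin is not read directly off an image. It comes from a rule that combines the sources of motion, fixes how much of the motion to cover, and moves from individual patients to a general value. None of these three choices is written down, and sections 5.2.8, 6.2 and 6.3 all stop at motion, position or dose. Section 5.2.2 also places the estimated margins next to the physician's per-patient expansion without saying which of them is the endpoint. Section 6.3 contours the PTV on CBCT, although the PTV already contains a margin, while 5.2.8 contours the tumour.

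The stake would be a reported result that two analysts could put at different values from the same images, with the rule chosen after the data are seen.

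**Working it through.** The plan states no margin, so there is no figure to reproduce. The question is how far the unwritten choices could move the result, and whether that matters to the study's conclusions.

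**Inputs.** From the documents: 5 mm limits on inter- and intra-DIBH tumour variation (4.1, step 4), 10 patients (6.0, 6.2), and a 50% completion criterion (6.0), which is 5 of 10. Assumptions, not in the documents: the three combining rules and the meaning of 5 mm.

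**Step 1: combining two components a and b at the limits.** The rules are max(a, b), sqrt(a² + b²) and a + b.

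| Reading of 5 mm | a, b (mm) | Larger | Root-sum-of-squares | Sum |
|---|---|---|---|---|
| One-sided displacement, same axis | 5, 5 | 5.0 | sqrt(50) = 7.1 | 10.0 |
| Centred peak-to-peak range | 2.5, 2.5 | 2.5 | sqrt(12.5) = 3.5 | 5.0 |

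Section 4.1 speaks of variation and 5.2.2 of amplitude. Section 5.1.8 uses a tolerance around the first setting for the surface, and a limit in one direction for the tumour. The one-sided reading therefore has direct support only for surface repeatability. These are also values at a screening ceiling, so they are not expected margins.

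**Step 2: the ratio.** With r the smaller component divided by the larger, sum ÷ larger = 1 + r. This is 2.0 at r = 1, 1.5 at r = 0.5 and 1.2 at r = 0.2. Root-sum-of-squares ÷ larger = sqrt(1 + r²), which is 1.41, 1.12 and 1.02. Twofold is the extreme case.

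**Step 3: from patients to a study value.** The largest of n patient values is expected to cover n/(n + 1) of further patients, with a 95% lower bound of 0.05^(1/n).

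- n = 10: 10/11 = 91%, lower bound 74%.
- n = 5: 5/6 = 83%, lower bound 55%.

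The mean covers about half if values are symmetric. A between-patient SD has 95% limits of sqrt(df/chi-square quantile) times its estimate: 0.69 to 1.83 with 9 df, and 0.60 to 2.87 with 4 df. The upper limit is 1.83/0.69 = 2.7 times the lower one even with all 10 patients. Imprecision in an SD from so few patients is thus at least as large as the twofold difference between rules.

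**Step 4: an illustrative spread (assumed).** With both components uniform on 1 to 5 mm in 10 patients, the average results are 3.7 mm (mean of the larger component), 4.4 mm (mean root-sum-of-squares), 6.0 mm (mean sum) and 8.5 mm (largest sum). The extremes differ 8.5/3.7 = 2.3-fold, but that compares an average of one component with a maximum of sums, which are different targets.

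**Step 5: would a fixed formula settle it?** Take a natural candidate: |M| + 1.96 × sqrt(S_B² + S_inter² + S_intra²), where M is the group mean offset, S_B the between-patient SD of patient means, and the other two terms are the SDs between and within holds.

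- The upper tail beyond this limit is 2.5%. The opposite tail falls from 2.5% at M = 0 towards 0 as |M| grows. Nominal coverage is therefore 95% to 97.5%, not a fixed 95%.
- Equal weight for between-patient and within-patient SDs, and the multiplier itself, are matters on which experts differ.
- The pre-treatment CBCT is used to align the patient (4.1, 5.2.5). Positions before alignment include setup error that is then corrected; positions after alignment are partly set to zero; the CBCT before the last beam is a third quantity.
- The screening images may show the diaphragm instead of the tumour (4.1, step 3). They also precede the planning CT, so no planned position exists for them.

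**Step 6: the other textual points.** Contouring the PTV in 6.3 fits the dose evaluation described there, and tumour position is named separately in the same section. Nothing requires the PTV contour to be the input to the margin. Section 4.1 already assigns the CTs at shifted levels to the level-position correlation.

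**The case for a change.** The strongest case for a change is that being a pilot excuses the absence of a hypothesis test but not of an estimator: the margin is itself something the study sets out to report. The rule is absent, the twofold ratio for equal components holds under either reading of 5 mm, and the undefined 5 mm widens the gap. A paragraph in 6.3 would need no new visits.

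Much of this stands. No section gives an estimator, an axis definition, a coverage level or a pooling rule, and the text does not say whether the endpoint is one study value or a set of per-patient margins. What does not stand is the step to a needed correction. No stated rule gives a wrong result. A single study-level margin is itself an inference, since 5.2.2 speaks of margins in the plural inside a per-patient planning step. A paragraph that really closed the question would have to settle weighting, coverage, alignment status and surrogate images, and the documents give no basis for preferring one answer.

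**Conclusion.** The concern describes a real lack of detail but does not call for a change. This is a descriptive 10-patient pilot without a formal sample size. The motion data are named, most have a stated purpose, and turning them into a margin is routine work for which an analyst would choose a recognised recipe and state it in the report. Because the motion components can be reported beside the margin, a reader who prefers another recipe can apply it.

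The size of the open choice is modest and conditional: 5.0 to 10.0 mm at the screening limits if 5 mm is a one-sided displacement on a common axis, 2.5 to 5.0 mm if it is a centred peak-to-peak range, and a ratio between rules of 1.2 to 2.0 for the relative sizes shown. All of these rest on combining rules that the documents do not name. The 50% completion criterion in 6.0 does not use the margin, so the feasibility conclusion is the same under any rule.
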